1. PURPOSE OF STUDY

The purpose of this study is to test the feasibility of a telehealth Dyadic Life Review (DLR), adapted from individual Life Review Therapy, with caregivers of older adults with advanced cancer, including those with Mild Cognitive Impairment (MCI). The study will enroll dyads of caregivers and older patients with advanced cancer and dyads of caregivers and patients with advanced cancer and Mild Cognitive Impairment (MCI). Life Review Therapy has only been delivered individually and there are no dyadic mental health interventions designed to target the mechanism of communal coping and reduce distress and emotional health outcomes in both older patients with advanced cancer and their caregivers. This innovative pilot study will gather data to test the feasibility of adapting Life Review Therapy to be delivered as a dyadic life review (DLR) and examine pre-post intervention changes in caregiver psychological distress.

1.1. Objective and Specific Aims (40 patient/caregiver dyads):

Objective: The research team will adapt and refine a dyadic life review intervention for older patients with advanced cancer, older patients with advanced cancer and MCI, and their caregivers. A mixed methods (i.e., integration of qualitative and quantitative data) approach will be used to gain understanding of the usability and feasibility of a telehealth DLR intervention with older adults with advanced cancer and their caregivers and examine effects on distress and emotional health in both the patient and caregiver.

1.2 Primary Aim:

1.2.1 To evaluate the feasibility of the dyadic life review intervention in older patients advanced cancer, with or without MCI, and their caregivers by determining consent rate, intervention adherence rate, and patient/caregiver acceptability. Hypothesis: We will achieve a dyad consent rate of 70%, dyad intervention adherence rate of 70%, and the intervention will be generally acceptable by dyads (determined from semi-structured interviews).

1.3 Secondary Aims:

1.3.1 To examine the pre-post change in the primary outcome of caregiver self-reported psychological distress, and secondary outcomes of caregiver loneliness, relationship satisfaction, and mental health outcomes, and changes in the associations between patient and caregiver distress.

1.4 Mixed Method Aim:

1.4.1 To enhance understanding of the usability of a telehealth based DLR intervention for older patients with advanced cancer and MCI, older patients with advanced cancer and MCI, and their caregivers and gain feedback on the intervention from separate semi-structured interviews of patients and caregivers. Integration will occur by using the qualitative data from semi-structured interviews to explain changes in the caregiver outcomes. The interviews will provide explanation for changes or lack of changes in the quantitative measures seen.

1.5 Exploratory Aims:

1.5.1 To explore the feasibility of collecting heart rate variability (HRV) from older patients with incurable cancer, MCI, and feasibility of collecting HRV from their caregivers.

1.5.2 To explore relationships between measures associated with the target mechanism model of communal coping to inform future development of a single communal coping measure in older patients with advanced cancer and their caregivers.

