Qualitative Data Analysis: Semi-structured interviews will be audio-recorded and transcribed into MAXQDA software for coding and analysis. Abductive analysis will be used to code transcribed interviews and extract themes. Two independent coders will code the data until thematic saturation is achieved. Coding will be compared and discrepancies resolved through an iterative process and achieving consensus. Semi-structured interviews will gather information about the acceptability of the intervention, perceptions of the dyadic approach to the interventions, and evaluate patient and caregiver perceptions of communal coping. A sub-group coding analysis will be performed to examine any differences in responses between older patients with only advanced cancer and their caregivers and older patients with both advanced cancer and MCI and their caregivers.

Integration: Qualitative and quantitative data, including baseline and follow up measures and

transcribed semi-structured interviews, will be integrated to develop a more complete understanding of the feasibility of a telehealth DLR intervention in this unique population and to gain understanding of the patient and caregiver experiences and gather thick descriptions about barriers and facilitators for the intervention. The qualitative data can provide explanatory data for any changes in the quantitative measures from pre to post intervention for both patients and caregivers.

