
Interview Script for Patients/Caregivers:

Interviews will cover several broad topics; interviewers will probe participants' responses for more detail as needed.

The same questions will be asked of both patients and caregivers, who will be interviewed separately. Names will be used wherever possible in place of bracketed terms.

1. "What are some strengths you see in this type of intervention?"
 - a. "What did you like most about the intervention?"
2. "What are some limitations you see in the current intervention you were provided information about?"
 - b. "What did you dislike about the intervention?"
3. "How do you feel about the length of the total intervention?"
4. "How do you feel about the length of each session?"
5. "How suitable is this intervention give your current demands and daily responsibilities?"
6. "What, if any, are memories or experiences you feel you would not want to share with [caregiver/patient]?"
7. "What, if any, are some memories or experiences you feel are most important to share with your caregiver?"
8. "What were your impression of the first half of the intervention (weeks 1-4), how did you feel about sharing about your childhood, adolescents, and young adulthood?"
9. "What were your impression of the second half of the intervention (weeks 4-8), how did you feel about sharing about middle age and more recent memories and experiences?"
10. "What would you have changed about this dyadic life review intervention?"
11. How did this intervention help your relationship with your partner?
12. "How do you cope with this illness?"
 - a. "Have [repeat identified coping strategies] changed since doing this dyadic life review?"
 - b. "If so, how have they changed?"
13. "What does coping look like between you and your partner?"
 - a. "Can you give examples of what that looks like?"
14. "If you experienced loneliness or a sense of isolation before this, how did that change during the intervention?"
 - a. "If these experiences did change for you, what helped this to change?"
15. "If you're willing, what were some things you and [caregiver/patient] talked about on the way home from the session or the night after that session?"

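### The interview script does not ask directly about the video and tablet experience or about change in distress, so two parts of the Mixed Method Aim rest on what participants volunteer

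*Combined protocol and SAP*

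**What the plan says.** Section 1.4.1 gives the interviews three jobs. The first is "To enhance understanding of the usability of a telehealth based DLR intervention". The second is to "gain feedback on the intervention from separate semi-structured interviews of patients and caregivers". The third is explanatory: "Integration will occur by using the qualitative data from semi-structured interviews to explain changes in the caregiver outcomes". The aim adds that the interviews should also account for an absence of change.

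Section 1.3.1 identifies the outcomes to be explained: the "primary outcome of caregiver self-reported psychological distress, and secondary outcomes of caregiver loneliness, relationship satisfaction, and mental health outcomes".

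The Data Analysis Plan, section 16.2.3, describes the interview content: "Semi-structured interviews will gather information about the acceptability of the intervention, perceptions of the dyadic approach to the interventions", together with perceptions of communal coping. It also plans a sub-group coding analysis that compares dyads with and without MCI.

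The instrument is the Interview Script for Patients/Caregivers, printed after the reference list. It has 16 numbered questions, put to both members of the dyad separately, and it tells interviewers to probe answers for detail. Question 15 asks "what were some things you and [caregiver/patient] talked about on the way home from the session", and then offers the night after the session as an alternative. Sections 3.3, 4.2 and 8.2 have all sessions delivered by video-conference, with participants encouraged to join from home or another private place.

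**The concern.** The aim names two things the interviews must deliver, and the script has no direct question on either. One is how people managed with a remotely delivered intervention, that is, the tablet, the log-in and the video call. The other is why caregiver distress did or did not move.

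Both matter for this design. The trial is single-arm and pre-post, so there is no control group to help interpret a change in distress, and participants' own accounts are the planned source of explanation. Telehealth delivery is part of what is being tested for feasibility. Adherence is defined in section 16.2.1 as completing all 8 sessions, yet the script never asks whether technology got in the way.

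If a topic is not put to everyone, its absence from a transcript has several meanings: no difficulty, no change, or not asked. Themes built on such material cannot be compared reliably across interviews or between the MCI and non-MCI groups.

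**Working it through.** The plan gives no figure on this point. Its one power statement concerns consent and adherence rates and has no bearing here. The check is a comparison of the script with the aim.

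**Step 1. Sort the 16 questions by content.**

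| Content | Questions | Count |
|---|---|---|
| General feedback: strengths, limitations, total length, session length, fit with daily demands, what to change, anything else | 1–5, 10, 16 | 7 |
| Memories, and feelings about sharing them | 6–9 | 4 |
| Relationship, individual and shared coping, loneliness | 11–14 | 4 |
| Conversation after a session | 15 | 1 |

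Total: 7 + 4 + 4 + 1 = 16.

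**Step 2. Search all questions and sub-prompts for the two topics.**

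- Stems for tele-, video, tablet, Zoom, technology, usability, online and internet: 0 occurrences.
- Stems for distress, stress, anxiety, depression and mood: 0 occurrences.
- For contrast, loneliness occurs once, isolation once, relationship once, and the coping stem three times.

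**Step 3. Set the aim beside the script.**

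- *Feedback on the intervention*: covered by the seven general items.
- *Usability of a telehealth DLR*: length and suitability (questions 3–5) bear on usability in a broad sense. Nothing asks about the technology.
- *Explaining caregiver outcomes*: loneliness is asked about as change, with a follow-up on what helped (question 14). Coping is asked about with a follow-up on change (question 12). Relationship is asked about in terms of help received (question 11). Distress, the primary outcome in section 1.3.1, is not asked about.

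The script therefore asks directly about a secondary outcome, loneliness, but not about the primary one.

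**Step 4. Look for cover elsewhere.** The list of interview topics in section 16.2.3 includes neither technology nor distress. The measures tables in section 8.1 contain no usability instrument. The Distress Thermometer and Problem List is given to both partners before and after the intervention and records sources of distress, but it does not ask what the person thinks produced a change.

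**Step 5. Extent.** 40 patient interviews + 40 caregiver interviews = 80, all using the same script. With at least 20 MCI dyads, at least 20 × 2 = 40 of these feed the MCI side of the sub-group comparison.

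**Step 6. Question 15.** Its first clause presumes travel from a session. Its second clause, about the night after, does not, so a dyad that stayed at home can still answer.

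**The case against.** A reader might infer from the zero counts that the Mixed Method Aim cannot be answered at all. The documents do not support that:

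- Feedback is one of the aim's three parts, and the script covers it well.
- The aim speaks of caregiver outcomes in the plural, and relationship and loneliness are among those in section 1.3.1.
- The interviews are semi-structured with probing allowed, so the items on limitations, dislikes, suitability and desired changes could bring out trouble with the video or remarks about distress.
- Section 8.1 says the interviews focus on experiences around the telehealth intervention, and the integration paragraph of section 16.2.3 refers to the feasibility of a telehealth DLR and to barriers and facilitators.
- The documents do not define usability as handling of technology, so it would be wrong to say that no question touches usability.

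A reader might also take question 15 as yielding only useless answers. Its alternative clause rules that out; it is a wording mismatch.

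All of this stands, and it limits the point. It does not remove it. Probing deepens what a participant has raised and does not oblige the interviewer to open an unlisted topic. Either the PI or a trained coordinator may conduct the interviews (section 8.2), so unscripted coverage may differ between interviewers. The general commitments in sections 8.1 and 16.2.3 are not carried into any question. The Problem List gives sources of distress at two time points, which helps, but section 1.4.1 assigns the explanation of change to the interviews.

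**Conclusion.** The concern holds in limited form. The script has no direct question on the video or tablet experience and none on change in distress: 0 of 16 questions in each case, across all 80 planned interviews. The aim remains partly answerable, since general feedback, relationship, coping and loneliness are addressed. The two parts named here would be supported only by volunteered remarks and discretionary probing. Silence on them could not be interpreted, and differences between MCI and non-MCI dyads could not be assessed reliably.

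This rests on two assumptions: that interviewers follow the script as printed, and that no separate probe list exists outside the documents. How many participants would raise either topic unprompted cannot be estimated from the documents, so the loss of information is not quantified. The gap lies in the script and the topic list. The aim itself needs no change.

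**What to change.** Before interviews begin, amend the script and section 16.2.3:

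1. Add a neutral item or standard probe for every participant on using the tablet and video for the sessions: what worked, what did not, and what help was needed.
2. Add a neutral item or standard probe, for example: *Over the weeks of the sessions, did your level of distress or stress change, or stay the same? What do you think contributed?* Offering both answers matters, because the aim covers lack of change too.
3. Reword question 15 to refer to talk *after a session ended or later that day*.
4. In section 16.2.3, add telehealth usability and change in distress to the interview content and to the codes, including those used in the MCI sub-group comparison.

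The cost is a minor script amendment, two sentences in section 16.2.3 and a few extra minutes per interview, with no additional visits, staff or participants. The downside is slightly longer interviews for people who may tire. The missing material could not readily be recovered once the interviews are done.

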2. BACKGROUND AND RATIONALE

Older patients with cancer will make up 60% of all cancer diagnoses by 2035.¹ The increase in older patients with cancer places more burden on caregivers.² Advanced cancer brings multiple challenges in each area of life for both older patients and caregivers. Cancer caregivers take on multiple domains of care, contributing to loneliness and relationship distress, with caregivers older than 50 experiencing more adverse mental and physical health outcomes.³ Supportive care interventions should involve caregivers.

Older adults with cognitive impairment and advanced cancer and their caregivers experience a vicious cycle of reciprocal distress, depression, and anxiety.⁴ It is estimated that 67% of patients over 65 will make up the new cases of cancer between 2010 and 2030.¹ Older patients with cancer also present with comorbidities and other age-related conditions, such as Mild Cognitive Impairment (MCI) or dementia. These conditions place an immense burden on cancer caregivers.⁵ Cancer caregivers support multiple areas of life for patients with cancer, including but not limited to medication management, treatment appointments, activities of daily living (ADLs) and instrumental activities of daily living (iADLs), financial needs, and emotional support.⁶ Considering the reciprocal distress and emotional health between patients and caregivers, and compounded needs of older patients with advanced cancer who have cognitive impairment, interventions targeting both the patient and caregiver dyad are needed. However, few mental health interventions have been adapted to this growing but vulnerable dyad that considers the trajectories of relationship satisfaction and loneliness in patient/caregiver dyads in this context where needs are immensely high.

2.1 *MCI and Cancer:*

MCI is prevalent in older patients with advanced cancer. This unique population of older patients with both advanced cancer and MCI and their caregivers have very high needs that are currently unmet. In a large nationwide study of older patients with advanced cancer, 33.5% met criteria for cognitive impairment.⁷ Studies suggest caregivers of older adults with cognitive impairments experience burden,⁸ relationship distress,⁹ and loneliness. Considering the combination of MCI and advanced cancer, the responsibilities of caregivers are compounded, potentially leading to more significant distress and worsening loneliness.

2.2 *Life Review Therapy and Outcomes for Older Adults:*

Older patients with MCI and advanced cancer present a compounded burden on caregivers, with reciprocal distress worsening emotional health and quality of life for both patients and caregivers. Studies suggest a major gap in interventions for older patients with MCI and advanced cancer.¹⁰ Intervention studies to date have focused on prevention of cognitive decline or early identification of

cognitive impairments.^{11,12} However, no studies focus on loneliness and distress of caregivers in this clinical context. Life Review was developed in 1968 and has been repeatedly shown to improve multiple emotional outcomes.¹³ Life Review therapy has been used in older adults in community settings, improving quality of life and reducing depression.¹⁴ In older adults with cognitive impairment, Life Review improved cognitive functioning.¹⁵ Additionally, Life Review therapy has been combined with memory specificity training demonstrating the Life Review is feasible in older patients with memory decline.¹⁶ A patient/caregiver DLR intervention could promote a communal coping mechanism and result in improved emotional health for both caregivers and patients.

2.3 *Dyadic Life Review Intervention:*

The traditional Life Review Therapy¹⁷ uses an 8-week, structured approach, with each session focused on a period of the life span, such as, childhood, adolescence, and so on. The intervention is often applied chronologically, but with flexibility for clinical judgements to explore other time periods that may arise for patients. For this proposal, Life Review Therapy will be adapted to be delivered dyadically, by the PI, a licensed mental health counselor and other trained clinicians with expertise in care of older adults, specifically for the older patient with advanced cancer and cognitive impairment and caregivers at risk or experiencing loneliness. The Dyadic Life Review (DLR) intervention will be delivered by one of three licensed mental health clinicians via videoconferencing over eight sessions. The goal of DLR is to enhance the dyad's communal coping and thereby reduce the loneliness and relationship distress experienced by both the older patient and caregiver. Communal coping is a process that enhances the dyad's joint resilience in supporting and managing the illness.⁶ Life review therapy has been found to reduce depression in older adults¹⁴ and promote emotional health and quality of life in patients with cancer in palliative care.¹⁸ Life review therapy combined with memory training has shown improved emotional health and cognitive functioning in older patients with cancer.¹⁶ Reminiscence therapies, which have similar processes and mechanisms to life review therapy improves cognitive functioning, anxiety, and depression in older adults with cognitive impairments.¹⁹ The vulnerable population of older patients with cancer and cognitive impairment may benefit from a DLR intervention as the intervention supports the patient/caregiver dyad in promoting communal coping, reducing loneliness and distress in both patients and caregivers, and supporting cognitive functioning in patients.

2.4 *Heart Rate Variability and Psychosocial Assessments:*

Studies have demonstrated a link between heart rate variability as a physical measure that correlates with the response to stressful life events.²⁰ Additionally, heart rate variability has been shown as an effective measure for a person's stress resilience.²¹ Recent studies have measured HRV in patients with cancer as a marker of distress,²² and utilized HRV as a mechanism for a biofeedback intervention to support patients with cancer in regulating stress and emotions.²³ However, no studies have explored HRV in older patients with cancer and their caregivers. This exploratory aim could support the further adaptation of patient and caregiver (dyadic) interventions and results could help power future studies.

The proposed study adapts and refines a well-established Life Review intervention to be used in a telehealth dyadic format to test the feasibility of using a telehealth dyadic life review intervention. Caregivers are an integral part to the management and navigation of advanced cancer in older patients. Additionally, when older patients with advanced cancer have MCI, caregivers take on even more roles to support the older patient's everyday life and long-term care. Intervention studies have examined preventative interventions to stall

cognitive decline, as well as interventions for identifying cognitive decline in patients with cancer. There are no studies that have engaged the caregivers of older patients with advanced cancer and MCI in the intervention design. Further, the use of a video-conferencing technology allows the intervention to be scalable. Many older patients with cancer and caregivers receive care and treatment from community clinics. Additionally, with the current state of the COVID-19 pandemic, delivering the DLR intervention provides an opportunity to test the feasibility of a telehealth intervention to promote safety as well as accessibility to older patients and caregivers in community settings.

3. ADMINISTRATIVE ORGANIZATION

Research locations:

3.1 The setting of this study will be Wilmot Cancer Institute (WCI) and Highland hospital. The WCI and Highland hospital site is the largest provider of cancer care across 16 counties in upstate New York. The WCI has an established infrastructure for conducting clinical research. WCI provides sources of collaboration, research training programs, weekly grand round presentations, and highly productive special interest research groups.

3.2 Rochester Roybal Center for Social Ties and Aging Research: The Rochester Roybal Center for Social Ties and Aging is funded through an NIH P30 grant and National Institute of Aging with the mission to support the development of behavioral interventions targeting the improvement of social connectedness for caregivers of family members with dementia. The Roybal Center will provide STAR resources to support caregiver assessments.

3.3 DLR participation will take place through video-conferencing. Participants will be encouraged to participate from their home or other private location. Wherever the location may be, the PI or other trained licensed mental health clinicians who are conducting the DLR intervention will ensure privacy in a private room with a closed door. Participants will be provided with a HIPAA compliant tablet to use for participation in the intervention activities and the intervention will be delivered using HIPAA compliant video-conferencing technology provided by the University of Rochester. The coordinator will be in touch with patients by phone throughout the length of the study. The study coordinator will help organize the scheduling/rescheduling of baseline assessments, DLR session, and follow-up assessments and interviews, and will be available for any patient or caregiver questions.

